2.1. Study design

The primary aim of this randomized trial is to test whether the Virtual Advisor intervention is as efficacious as the Peer Advisor intervention in promoting significant 12-month increases in weekly minutes of walking—a form of moderate-intensity activity that is readily accessible and appealing to substantial numbers of midlife and older adults across the socioeconomic spectrum.^{3,23} The study employs a cluster-randomized design of community centers located in neighborhoods with at least 20% midlife and older Latino residents.²⁴ In addition to location, other factors that were considered in choosing community centers included interest and willingness of center staff to participate in the study, appropriate space to accommodate computer equipment for the Virtual Advisor or Peer Advisor sessions, and a steady flow of Latino midlife and older adults who utilize the center's regular programs and services. Community centers were matched by geographic location and randomized to either the Peer Advisor or Virtual Advisor intervention arm. The comparative effectiveness of these two interventions constitutes the major objective of the study and is the focus of this paper. To take

advantage of the study design to begin to explore new dietary intervention strategies in this underserved population, an additional pilot substudy is also underway. As part of this pilot substudy, two other similar community centers (one in each county in which the study is located) have been selected to receive culturally adapted dietary information via mail and face-to-face modalities across the one-year study period.

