2.14. Randomization of community centers to study arms

Block randomization by county locale was used to assign ten community centers to the two major study arms. Centers were randomized in pairs by locale via coin toss by staff not involved in study assessment or intervention procedures. Allocation concealment was in place for each block of centers during the randomization process to minimize selection bias with respect to subsequent blocks. Assessment staff members are blinded to randomization assignment and masked to prior assessment data for each participant.

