2.15. Sample size calculation and data analysis plan

Sample size estimates have been developed to test the study's primary question related to whether the Virtual Advisor intervention is no worse than the intervention delivered by trained human advisors, i.e., a test of non-inferiority.⁶³ Using a two-tailed 95% confidence interval on the effect size (Cohen's d), the threshold of clinical significance between the two treatments, Δ , has been developed to demonstrate clinical noninferiority of the new intervention (Virtual Advisor) if the confidence interval lay completely above $-\Delta$, while clinical noninferiority of the Peer Advisor intervention will be demonstrated if the confidence interval lay completely below $+\Delta$. In this trial, the effect size (Cohen's d) is the standardized difference between the change in walking minutes/week over the 12-month intervention period. The critical value of Δ is based on a clinically meaningful difference between arms of 30 minutes of walking per week,³ and a within-arm standard deviation of 90, accounting for clustering within centers.⁶⁴ The noninferiority margin was based on a clinically meaningful difference, in one direction, between arms of 30 minutes walking/week,³ and a within-arm standard deviation of 90, accounting for clustering within centers ($\Delta=.30$).⁶⁴

We calculated that a sample of 112 per arm (224 total) would provide 80% power to demonstrate noninferiority between the two interventions using a simple pre-post analysis. We plan to use a mixed-effects linear regression model. Mixed-effects linear regression effectively addresses both missing data and early dropout in "intent-to-treat" analysis.^{65,66} In addition, the multiple assessment time points in the trial (at baseline, 6 months, and 12 months) will serve to provide more detailed information on changes over time relative to studies using pre-post assessment only.⁶⁷ Twenty-one additional participants were recruited to protect against loss to follow-up. Similar mixed-effects

linear regression techniques will be used to address the secondary outcomes of interest, e.g., intervention impacts on well-being variables across the study period.

3. Results

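### Section 2.15 states 80% power at 112 per arm, but its own 95% interval rule gives about 70% (true difference of 0 assumed)

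*Combined protocol and SAP*

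**What the plan says.** Section 2.15 of the combined protocol and SAP sets out a noninferiority test on the 12-month change in weekly walking minutes. The decision rule begins "Using a two-tailed 95% confidence interval on the effect size", and the Virtual Advisor is noninferior if the whole interval lies above minus delta. The margin is 30 min/week. The SD is given as "a within-arm standard deviation of 90, accounting for clustering within centers", and delta is printed as .30. The sample size statement is "We calculated that a sample of 112 per arm (224 total) would provide 80% power", and that calculation was made "using a simple pre-post analysis". Twenty-one further participants cover loss to follow-up. No true difference between arms and no intracluster correlation (ICC) is stated.

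On the analysis, the section says "We plan to use a mixed-effects linear regression model" and supports this by missing data, dropout and the three assessment times. It does not list the model's terms.

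On the design, section 2.1 says "The study employs a cluster-randomized design of community centers" and "Community centers were matched by geographic location and randomized to either the Peer Advisor or Virtual Advisor intervention arm". Section 2.14 adds "Block randomization by county locale was used to assign ten community centers", with the coin toss made within pairs. Section 3.1 reports that one center was lost, leaving four in that arm and nine in all. Section 3.2 gives 245 enrolled, 123 and 122 by arm.

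**The concern.** A two-tailed 95% interval compared with a single bound is a one-sided 2.5% test. The printed 112 per arm looks like the answer for a one-sided 5% test. If so, the trial has less chance of showing noninferiority than readers are told, and a failure to show it could be misread as evidence that the Virtual Advisor is worse. At 112 per arm the half-width of the 95% interval is 1.960 × 12.03 = 23.6 min/week, so the observed difference must be better than about −6.4 min/week to clear the margin.

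A lesser matter is that clustering appears in section 2.15 only through the planning SD. An inflated SD in a sample size formula does not put the center into the analysis model, and the text does not say how the center enters or what reference distribution will be used with nine centers.

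**Working it through.** **Inputs.** From section 2.15: margin 30 min/week, SD 90 (taken as already including clustering, as the section says), 112 per arm, two-tailed 95% interval. From sections 3.1 and 3.2: nine centers; 123 and 122 enrolled. Assumed: true difference d = 0, with a range in step 5.

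**1. Reproduce the printed sample size.** n per arm = 2 × (SD/margin)² × (z for alpha + z for power)², and 2 × (90/30)² = 18.
- One-sided .05: 18 × (1.645 + 0.842)² = 111.3, so 112. This is the printed figure.
- One-sided .025, which is the stated interval: 18 × (1.960 + 0.842)² = 141.3, so 142.

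**2. Power at 112 per arm.** SE = 90 × √(2/112) = 12.03, and 30/12.03 = 2.494.
- One-sided .05: Φ(2.494 − 1.645) = 80.2%.
- Stated interval: Φ(2.494 − 1.960) = 70.3%.

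**3. Printed delta.** 30/90 = .333, not .30. A delta of .30 is a margin of .30 × 90 = 27 min/week, and 27/12.03 is about 2.245. Power at the stated interval is Φ(2.245 − 1.960) = 61.2%, and 80% would need 174.4, so 175 per arm. Even at one-sided .05, power is only 72.6%. The printed sample size therefore goes with 30/90.

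**4. All 245 analysed, no dropout.** SE = 90 × √(1/123 + 1/122) = 11.50. Φ(30/11.50 − 1.960) = 74.2%.

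**5. True difference.** Power = Φ((30 + d)/12.03 − 1.960). For d = −5, 0 and +5 min/week this gives 55%, 70% and 83%. To reach 80%, d must be 2.802 × 12.03 − 30 = 3.7 min/week in favour of the Virtual Advisor. Alternatively, with d = 0, the SD would have to be 30 × √56 / 2.802, about 80.

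**6. Sensitivity rows on center-level df.** Nine centers less two arm means leave 7 df. A two-level county term leaves 6. Power comes from the noncentral t distribution with noncentrality 2.494 at d = 0 and critical values 2.365 (7 df) and 2.447 (6 df). No credit is taken for the 6-month visit or for variance removed by locale.

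| Reference | 112 per arm, d = −5 | d = 0 | d = +5 | All 245, d = 0 |
|---|---|---|---|---|
| Normal | 55% | 70% | 83% | 74% |
| 7 df | 43% | 57% | 71% | 61% |
| 6 df (county fitted) | 42% | 55% | 68% | 59% |

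With all ten centers (8 df) the 112-per-arm figure at d = 0 would have been 59%.

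**7. If the center were left out of the model.** At a true difference of −30, the one-sided error is about Φ(−1.960/√DEFF), where DEFF = 1 + (m − 1) × ICC. With four and five centers, m averages about (30.75 + 24.4)/2 = 27.6. At assumed ICCs of .01, .02 and .05, DEFF is about 1.27, 1.53 and 2.33, and the error is about 4%, 6% and 10%. A simulation of 40,000 trials gave 4.0%, 5.7% and 10.0%. At ICC 0 the error stays at the nominal 2.5%.

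**The case against.** Section 2.15 states no true difference, so 80% could be right under an assumption that was not printed. This is possible, but it needs a true advantage of 3.7 min/week for the Virtual Advisor, and 112 is exactly the answer for a one-sided 5% test at zero difference. Whether the interval level or the power is the misprint cannot be settled from the text, so the request has to be to reconcile them. The three-visit model may also be more precise than a pre-post comparison. No correlation between visits is given, however, and the 80% was itself claimed for the pre-post comparison, so 70% is the like-for-like figure.

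Two stronger readings are tempting.

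- A reader might infer that the true power is 55% to 57%. Section 2.15 states no center-level df. The figures rest on a center lost after randomization and, for 55%, on a county term that the plan does not require. They also credit nothing for the extra visit or for locale. They are sensitivity figures.
- A reader might infer that the primary analysis ignores clustering and will declare noninferiority too often. The documents do not show this. Section 2.1 declares cluster randomization, and section 2.15 mentions clustering within centers twice before planning a mixed-effects model, so a center effect is the natural reading. Error rates of 4% to 10% need both an omitted center and an ICC above zero, and the documents give no ICC.

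What stands on the model is that its terms are not written out.

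**Conclusion.** The power statement is wrong as written. At the plan's own 95% interval, 112 per arm gives about 70%, ten points below the stated 80%. With the printed delta of .30 it gives about 61%. The result assumes a true difference of 0, an SD of 90 that already includes clustering, and a normal reference. The mismatch does not depend on the number of centers. It affects how the result will be read; it changes neither the interval nor the noninferiority decision.

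The missing model terms are a secondary point that should be fixed, because centers were the randomized unit and only nine remain. How locale enters (county, pair or neither) is a clarification only.

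**What to change.** **Power statement.** Reconcile the interval level, the margin (.30 against 30/90) and the power. If the two-tailed 95% interval is kept, restate power as about 70% at 112 per arm, or about 74% if all 245 are analysed. Use the .30 figures instead if that margin is the intended one. List the true difference as an assumption with a range such as −5 to +5 min/week, and show the 7 df and 6 df results as sensitivity rows with their caveats. Enrol no one further. The cost is a few lines of text and a short table, and a less favourable stated power.

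**Model (secondary).** Write the primary model with a random center effect that acts on 12-month change. If change or baseline-adjusted 12-month walking is modelled, a center intercept does this. If all visits are modelled, a center-by-time effect is needed, because a center intercept alone cancels out of the arm-by-time contrast. Name a small-sample df method such as Satterthwaite or Kenward-Roger. State in advance whether and how locale enters; that choice is the sponsor's. The cost is SAP wording and a few lines of model code; the downside is a wider interval.

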3.1. Selection and description of study community centers

Ten community centers located in Santa Clara and San Mateo Counties, California with at least 20% Latino households (range = 21-55% Latino households) living within a one- to five-mile radius from the center were identified and expressed interest in serving as a study intervention site. These sites were block-randomized by locale to either the Peer or Virtual Advisor arms. Soon after recruitment, one center experienced unforeseen changes in its administration that disrupted center operations and precluded center participation in the study. To ensure comparable participant enrollment in each study arm, additional participants were enrolled at the remaining four community centers assigned to that intervention arm.

In each center, there were center staff who were willing to support the research team in reserving meeting space for clinical assessments, recruitment meetings, and, when relevant, Peer Advisor meetings. For the sites that received the Virtual Advisor, designated staff members were instructed on how to maintain the computer kiosk (i.e., refilling printer paper, providing minor technical support related to the computer such as making sure that it was switched on and that the touch screen remained clean, and contacting a member of the research team if needed.)

All participating community centers offered, as part of their usual activities, a nutrition program for older adults as well as nonphysical activity-oriented classes and activities, such as bingo, karaoke, and arts and crafts. Additionally, 89% offered weekly

physical activity classes and had at least one general computer available for older adults visiting their center.

3.2. Study participants enrolled and recruitment sources

A total of 245 participants are enrolled in the primary trial (Peer Advisor arm: n = 122; Virtual Advisor arm: n = 123). Participant baseline demographic and health characteristics are summarized in **Table 1**. The study participants range in age from 50 to 87 years, and 79% are women, with about half of participants reporting being married or living with a partner. The predominance of women is common in such health promotion intervention studies, as is the reluctance of participants, especially from such lower-income communities, to report their household incomes. Forty-four percent of participants have high school or lower levels of education.

The highest recruitment yield (88.7% of enrolled subjects) was obtained from the geographically defined and demographically targeted bilingual mass mailings aimed at the Census blocks surrounding the community centers. The total number of targeted letters mailed describing the study and inviting individuals to contact the study team for more information was 107,930. The total cost of the targeted mailing recruitment strategy equaled approximately \$69,900.00.

3.3. Results related to recruitment and enrollment of Peer Advisors

During the recruitment process for Peer Advisors, 230 individuals expressed initial interest, and 119 individuals were found to be eligible based on the study's Peer Advisor eligibility criteria. Of these individuals, 56 completed the Peer Advisor training requirement, and 36 initiated Peer Advisor activities with at least one participant. Over

the course of the intervention period, six Peer Advisors had to relinquish their peer advisor activities due to a move out of the area, medical illness, or the initiation of a new job which put constraints on their time. Their study participants were transferred successfully to other Peer Advisors with minimal difficulties.

4. Discussion

The COMPASS Trial is among the first studies to systematically compare the effectiveness of physical activity advice delivered by humans versus automated advisors in aging Latino adults. Insufficiently active Latino adults are at elevated risk for a variety of chronic diseases and conditions, yet have rarely been targeted for tailored physical activity advice and support using communication sources (i.e., trained peer advisors, virtual advisors) that have great potential for population transferability and reach. The use of community centers for intervention delivery provides a readily available intervention access point in many communities across the U.S., and the one-year intervention period will provide insights related to initial physical activity adoption and more sustained behavioral maintenance. The multi-faceted recruitment plan allows for a more diverse and potentially generalizable sample, and the particularly high yield of the targeted mass mailings is notable, given its less frequent use in a number of community-based research studies. At least one study has shown that personalized direct mailings can increase response rates for Latino adults relative to non-targeted approaches.⁶⁸ While community-based *promotores de salud* (i.e., lay or peer advisors) are a known and effective mechanism for health promotion in Latino populations, the method has been limited by the ability to scale. If the technology-enabled Virtual Advisor proves comparable and cost-sensitive relative to the Peer Advisor arm, it represents a

scalable and replicable solution that could be readily integrated into current community and senior center infrastructures.

While the primary aim of this trial is to compare the 12-month effectiveness of the Virtual Advisor relative to Peer Advisors, a similarly compelling goal is to explore, through the planned moderator analyses, which participant subgroups may do best with which type of intervention. Referred to as “the whiches conundrum”,⁶⁹⁻⁷¹ ascertaining how best to target different interventions to different subgroups of people represents among the most important challenges currently facing the behavioral health and precision medicine fields.⁶⁹ Similarly, the planned mediator analyses will provide initial information on which types of variables may be of particular importance for achieving intervention-related impacts on physical activity levels.

5. Conclusion

If the promising preliminary Virtual Advisor evidence obtained from the original pilot study²² is confirmed in this comparative effectiveness trial, this intervention will represent a potentially low-cost, readily accessible option that could be broadly disseminated across a range of community settings (e.g., clinics, pharmacies, libraries, residential settings). As such, it has substantial potential to reduce the health disparities gap by influencing a key health behavior in underserved populations.⁷²

HUMAN SUBJECTS

Note: All investigators participating in the proposed research have completed the Human Participant Protections Education for Research Teams certification process in compliance with NIH and Stanford University or Northeastern University guidelines.

I. Consent Procedures

Prior to undergoing the initial telephone or face-to-face screening, the screening procedures will be explained and individuals will give verbal consent to answer initial eligibility questions (age, ethnicity, proximity to community center). Those who are initially eligible will then proceed to an information session where the study activities and procedures will be explained in greater detail. If interested in continuing at that point, individuals will read and sign an informed consent form approved by the Human Use Committee at Stanford Medical School. This consent form will describe the study assessment and intervention components of the project, and their rights as research participants. The consent form will inform individuals that all information is strictly confidential and will not be released to anyone without their written consent. They will be reminded that as volunteers they can terminate their participation at any time without negative consequences. They will be provided information to contact the Medical Committee for the Use of Human Subjects in Research at Stanford Medical School.

II. Potential Risks

The potential risks involved in this project include psychological complications resulting from the assessment procedures or medical risks associated with moderate intensity physical activity programs in persons in this older age group.

Psychological risks of the evaluation. There is a remote risk that persons completing questionnaires focusing on behavioral or psychological content may become distressed. There is no evidence that any permanent psychological dysfunction has resulted from such assessments.

Medical risks of physical activity programs. The major risks of physical activity programs by initially inactive persons aged 55 years and over are orthopedic and cardio-respiratory. Orthopedic problems primarily are of the overuse variety and usually can be treated by rest and change in the mode of physical activity. Frequent minor problems can occur, including temporary soreness or irritation of muscles, tendons and joints. The likelihood of orthopedic and cardio-respiratory risks are greatly minimized through the use of a moderate-intensity physical activity program that involves mild to moderate-intensity walking, as proposed in the current study, and a supervised, individualized, progressive approach to physical activity as proposed in the current program.

III. Minimizing Potential Risk

Study assessments will be conducted at the community centers by extensively trained and supervised study staff.

Physical activity programs. To ensure participant safety in this study, we will apply the set of screening and oversight procedures that are recommended in the American College of Sports Medicine's (ACSM) guidelines and that we have used successfully in our research studies over the past 30 years. As recommended in the current ACSM guidelines, to screen potential participants for appropriateness for the physical activity program, we will have each individual complete the Physical Activity Readiness Questionnaire (PAR-Q), an extensively validated and used screening questionnaire that

has been used throughout Canada and the U.S. to screen individuals for community-based physical activity programs. If individuals answer 'yes' to any of the medically related screening items, they will be directed to get physician clearance prior to entry into the study. This protocol has been shown to ensure participant safety without creating unnecessary medical expenses and barriers to participation for persons not deemed at risk for physical activity-related complications---an important issue for the low-income population being targeted. The use of a mild form of physical activity (walking) also diminishes risk. In addition, participants will be regularly monitored for any level of physical discomfort or injury as part of the virtual advisor and lay advisor programs, and all subjects will be evaluated for adverse events as part of the study assessments conducted every 6 months using the standard forms approved for use by the Stanford Institutional Review Board.

The risks of injury resulting from participating in the prescribed physical activity programs will be minimized in several ways:

- Exclusion from the study of any person with overt cardiovascular or orthopedic disease.
- Individualized physical activity program aimed at slow, gradual progression of physical activity amount.
- The use of moderate-intensity physical activity programs, involving walking, for all study participants.
- Ongoing personalized instruction of participants as part of the evidence-based physical activity advisor programs.
- Ongoing attention to and advice related to the experience of physical discomfort during physical activity as part of both evidence-based physical activity advisor programs. (In addition, standard advice from the current U.S. Department of Health and Human Services' national physical activity recommendations

concerning physical activity safety is provided as part of the health education attention-control program.)

The content of the moderate-intensity physical activity program that is being targeted is commensurate with the current national guidelines for physical activity promotion in older adults.

Confidentiality of participant data. Confidentiality of participant data will be maintained by handling individual data by ID number, rather than by name; storing all individual data in locked file cabinets and secured, password protected electronic hard drives and data servers; and not disclosing individual data to anyone other than project staff, except as requested by the participant in writing.

Adverse event monitoring and reporting. Adverse events information will be collected at all assessment points and recorded on standard forms that have been used in our other studies. We will collect information on all potential types of adverse events, including musculo-skeletal soreness and injury, as well as major medical events including injuries or conditions that result in health care provider visits, hospitalization, etc. Consistent with NIH and Stanford IRB policy, adverse events will be promptly reported in writing to the NIH and Stanford IRB.

IV. Risks versus Benefits

We believe the risks involved with the proposed physical activity interventions and associated tests are very small. Our own experience in studies involving the assessments proposed and the encouragement of progressive, moderate intensity physical activity in screened participants in this age group has been very positive. We

are not aware of a single long-term adverse reaction to such physical activity programs among the over 3,000 study subjects we have monitored over the past 30 years.

We believe that all participants will benefit by learning (from the study questionnaires) about their health status and physical activity levels. Those who successfully improve their physical activity levels will have achieved desired goals. Over the study period, all participants will benefit from receiving health information.

We believe society will benefit from the results of this project in that it will inform further research aimed at developing effective and appropriate physical activity programs for under-served ethnic minorities. It will shed light on how best to deliver physical activity advice to enhance adoption and maintenance of PA among Latinos using state-of-the-art informational technology that could conceivably be utilized in a range of community and home settings, thus substantially broadening the reach of the physical activity counseling program to underserved populations at potentially lower-cost than traditional face-to-face or health care provider-delivered approaches. These are public health issues of immense proportions, particularly with the continued growth of the elderly segment of the U.S. population and the substantial prevalence of inactivity among that population segment. In summary, we believe the risks can be kept very low whereas the benefits to participants and society are quite substantial.

Data and Safety Monitoring Plan

In addition to ongoing (weekly) project oversight by our senior investigators, the project's Data and Safety Oversight Committee, will meet at regular intervals (e.g., semi-annually or more frequently as indicated) throughout the project period to provide input and feedback related to study recruitment and retention rates, study eligibility

determination issues, data completion rates, and adverse events. During the study, participants will regularly monitor any discomfort that they are experiencing from the moderate-intensity physical activity program (consisting of walking) and will report them to their physical activity advisor on a weekly basis. We will use this information to revise the interventions as necessary to ensure that any risks of injury or discomfort are minimized.

Table and Figure Descriptions

Table 1. Descriptive statistics for the trial sample and by randomization arm

[figure not shown]
Figure 1. Screenshot of the Virtual Advisor (“Carmen”)

Table 1
Descriptive statistics for the sample and by randomization arm.

Variable (categorical)	All		Virtual Advisor		Peer Mentor		Between group p value
Sex							
Women	193	78.8	98	79.7	95	77.9	0.73
Men	52	21.2	25	20.3	27	22.1	
Race/ethnicity							
Hispanic	241	98.4	120	97.6	121	99.2	0.71
Asian	3	1.2	3	2.4	0	0.0	
White	1	0.4	0	0.0	1	0.8	
Country of birth							
United States	100	40.8	53	43.1	47	38.5	0.01
Mexico, Central, South America	139	56.7	65	52.8	74	60.7	
Other	3	1.2	2	1.6	1	0.8	
Missing	3	1.2	3	2.4	0	0.0	
Marital status							
Married or living with partner	125	51.0	59	48.0	66	54.1	0.11
Not married or living with partner	118	48.2	63	51.2	55	45.1	
Refused	2	0.8	1	0.8	1	0.8	
Education							
Less than High School	62	25.3	27	21.9	35	28.7	0.42
High school	45	18.4	28	22.8	17	13.9	
Some college	80	32.7	39	31.7	41	33.6	
College	27	11.0	15	12.2	12	9.8	
Postgraduate	28	11.4	12	9.8	16	13.1	
Missing	3	1.2	2	1.6	1	0.8	
Household income							
< \$5000 to \$34,999	32	13.1	17	13.8	15	12.3	0.97
\$35,000 to \$49,999	23	9.4	11	8.9	12	9.8	
\$50,000 to \$74,999	30	12.2	16	13.0	14	11.5	
\$75,000 or greater	45	18.4	21	17.1	24	19.7	
Don't know, refused, missing	115	46.9	58	47.2	57	46.7	
Variable (continuous)	Mean	SD	Mean	SD	Mean	SD	
Age (yr.)	62.3	8.4	63.1	8.3	62.4	8.5	0.82
Years in US	47.4	17.0	47.7	17.2	47.1	16.8	0.80
Number in household	3.5	2.2	3.7	2.5	3.3	1.8	0.16
CHAMPS Q – baseline (min/wk.):							
Walking for exercise & leisure	45.9	91.6	48.0	98.1	43.6	81.4	0.71
Walking briskly	3.7	16.1	5.1	19.7	2.3	11.4	0.18

Moderate, vigorous activities	23.5	69.2	22.4	62.8	24.6	75.1	0.81
-------------------------------	------	------	------	------	------	------	------

Fig. 1. Screenshot of the Virtual Advisor (“Carmen”).

References:

1. IM, Shiroma EJ, Lobelo F, et al. Effect of physical inactivity on major non-communicable diseases worldwide: an analysis of burden of disease and life expectancy. *Lancet*. 2012;380(9838):219-229.
3. Physical Activity Guidelines Advisory Committee. *Report of the Physical Activity Guidelines Advisory Committee, 2008*. Washington, DC: U.S. Department of Health and Human Services;2008.
6. Silvia CA. Barriers to physical activity in the Hispanic community. *J Public Health Policy*. 2003;24(1):41-58.
